9.3 Study Population Data

The following demographic and baseline characteristics will be summarized by treatment group as follows: age, weight, gender, race and vital signs.

For continuous measurements such as age, the mean, median, standard deviation and range will be tabulated.

For categorical measurements such as gender, the frequencies will be computed.

9.4 Efficacy Analyses

9.4.1 Primary Efficacy Analyses

- Mean absolute change in haemoglobin level from baseline to 6 months after treatment with EPIAO/EPREX in parallel groups (g/dl).
- Mean absolute change in weekly epoetin dosage per kg body weight from baseline to 6 months after treatment with EPIAO/EPREX in parallel groups (IU/kg/week).

The ANCOVA will be performed based on the normality of data for mean change between baseline to 6 months of EPIAO and EPREX with center, Hb level and weight as covariates. The 95% confidence intervals will be calculated for the treatment differences and is compared with pre-defined acceptance ranges: ± 0.5 g/dl for haemoglobin.

The ANCOVA will be performed based on the normality of data for mean change in weekly epoetin dosage per kg body weight baseline to 6-month treatment with EPIAO and EPREX with center, Hb level and weight as covariates. The 95% confidence intervals will be calculated for the treatment differences and is compared with pre-defined acceptance ranges: ± 45 IU/kg/week for dosage.

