	
The SAS® package (SAS® Institute Inc., USA, and Version 9.2 or higher) will be used for statistical evaluation.
 
Descriptive statistics, such as mean, standard deviation, median, minimum and maximum values will be provided for the continuous variables and the number of observations and percentage will be provided for the categorical variables.

Statistical Analyses:	
Primary Endpoints
 
• Mean absolute change in haemoglobin level from baseline to 6 months after treatment with EPIAO/EPREX in parallel groups (g/dl).• Mean absolute change in weekly epoetin dosage per kg body weight from baseline to 6 months after treatment with EPIAO/EPREX in parallel groups (IU/kg/week) 
The ANCOVA will be performed based on the normality of data for mean change between baseline to 6 months of EPIAO and EPREX with center, Hb level and weight as covariates. The 95% confidence intervals will be calculated for the treatment differences and is compared with pre-defined acceptance ranges: ± 0.5 g/dl for hemoglobin.

The ANCOVA will be performed based on the normality of data for mean change in weekly epoetin dosage per kg body weight baseline to 6 months treatment with EPIAO and EPREX with center, Hb level and weight as covariates. The 95% confidence intervals will be calculated for the treatment differences and is compared with pre-defined acceptance ranges: ± 45 IU/kg/week for dosage.

Secondary Endpoints

- Proportion of subject's hemoglobin values are within 10 - 12 g/dl for the last 4 weeks of the period for assessment of treatment efficacy and safety (weeks 32-36)
- Proportion of subjects with any haemoglobin measurement outside the target range during the double-blind treatment period
- Mean hemoglobin and hematocrit levels every 4 weeks within treatment period (52 weeks)
- Mean doses of the study products (IU/kg/week) every 4 weeks throughout the study period (52 weeks)
- Incidence of blood transfusions

The appropriate descriptive statistics or frequency and percentages will be presented for the secondary end point. Other analysis will be carried out as deemed appropriate.

Safety Endpoints

- Incidence and nature of adverse events
- Incidence of drug related adverse events
- Clinically significant changes in the vital signs, physical and laboratory examination
- Number of subjects who prematurely withdrew from the study due to AE and SAE

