Mikhail A in his review “Epoetin Biosimilars in Europe: Five Years On” (2012), says that switching between an original reference ESA and a biosimilar (and possibly also switching between biosimilar versions of the same product) should be regarded as a change in clinical management. Clinicians need to be fully involved in such decisions (11). If clinicians wish to ensure that a given patient receives a specific biologic or biosimilar, they should prescribe by brand

name to prevent unintentional substitution by pharmacists and allow for effective pharmacovigilance.

Switching from epoetin alfa to SB309 increased the dose required by approximately 10–15% and transiently decreased the hemoglobin level by approximately 5%. Switching from SB309 to epoetin alfa reduced the dose required by around 10% and increased hemoglobin levels by approximately 10%. As in the correction phase study, a correction factor was introduced to correct for differences in protein content of the two ESAs being compared. In the maintenance phase study, this led to a widening of the revised 95% CI for dosage of 3.086–13.917 IU/kg/week. Again, the 95% CIs were within the modified acceptance range of ± 45 IU/kg/week. A further post-hoc analysis of the two 24-week, randomized, double-blind correction and maintenance studies and the 56-week, open label, follow-on study reported above evaluated the impact of switching hemodialysis patients with CKD between epoetin alfa and SB309 on hemoglobin concentration, epoetin dose and safety. In the maintenance study, 118 patients switched from epoetin alfa to SB309 and 121 switched from SB309 to epoetin alfa; 104 of the 121 patients switched back to SB309. Only 101 patients completed 12 weeks of follow-up treatment without apparent major protocol deviations. In the correction study, 249 of 268 patients switched from epoetin alfa to SB309. A total of 242 patients completed 12 weeks of follow-on treatment without any apparent major protocol deviations. Therapies were considered equivalent if the 95% CI of the mean intra-individual difference in hemoglobin concentration before and after the switch remained within the pre-specified equivalence limits (± 1.0 g/dL).

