1.5.3 Regulatory Compliance

The study protocol, subject information and consent form, the investigator brochure or written instructions to be given to the subject, available safety information, subject recruitment procedures (eg, advertisements), information about payments and compensation available to the subjects and documentation evidencing the investigator's qualifications should be submitted to the IEC or IRB for ethical review and approval according to local regulations, prior to the study start. The written approval should identify all documents reviewed by name and version.

Changes in the conduct of the study or planned analysis will be documented in a protocol amendment and/or the Statistical Analysis Plan (SAP).

The investigator must submit and, where necessary, obtain approval from the IEC or IRB and/ or Sponsor for all subsequent protocol amendments and changes to the informed consent document or changes of the investigational site, facilities or personnel. The investigator should notify the IEC or IRB of deviations from the protocol and serious adverse events occurring at the site in accordance with local procedures.

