5.1.7 Dosing Schedule, Selection and Timing of dosing

Study drugs have to be administered in strict accordance with approved protocol.

Treatment arm A

EPIAO group (test product) having 132 subjects will receive EPIAO, one to three times a week, intravenously for period of 52 weeks at the end of dialysis session

Treatment arm B

EPREX group (reference product) having 132 subjects will receive EPREX, one to three times a week, intravenously for period of 52 weeks at the end of dialysis session

The blood pressure will be monitored after the haemodialysis procedure and if the blood pressure is within the normal range then the study medication will be administrated by the study nurse or designee. If systolic pressure >160 mm of Hg, the blood pressure will be monitored after half an hour. If the BP does not decrease then the subject will be asked to come the next day for drug administration.

The dose will be adjusted individually to maintain haemoglobin at a level not exceeding 12 g/dl. The required dose will be calculated based on the haemoglobin.

Dosage adjustment:

Titration period:

During titration period, EPREX will be administered one to three times weekly as per last dose which subject received previously before screening, for subject who are already on treatment. EPREX will be administered one to three times weekly as per Hb value at screening and as per PI discretion. The dose received by the subject at screening will be taken as the "basic initial dose" for all subjects. An increase or decrease of 2000 IU per week will be allowed for dose adjustment to maintain subject's Hb value within target range (10 – 12.5 g/dl). At this point, the "stable dose" of EPREX for each patient will be determined. The stable dose of EPREX / EPIAO will be calculated as IU/kg/week before the start of the treatment period and captured in the eCRF. In substantiated cases, a prolongation of the titration period is allowed up to maximum of 4 to 5 months on a case to case basis which will be considered as extended titration period.

During treatment period, subjects randomized to EPREX arm will continue on an equivalent dose of EPREX as during the titration period. Subjects randomized to EPIAO arm will receive EPIAO treatment 1:1 dose conversed from that of EPREX during the titration period. If subject's Hb value is out of target range, an increase or decrease of 2000 IU per week is allowed for dose adjustment. The maximum allowable dose is 300 IU/kg/week.

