Treatment period:

The dose should be adjusted for each patient to achieve and maintain hemoglobin levels between 10-12 g/dl. The maximum dose of study drug is 300 IU/kg.

[figure not shown]
The investigator can adjust the dose by their own decision based on the best interest and safety of the subject and in any time

Two key factors will be considered for dose adjustment during the study period

1. Hemoglobin level at current visit
2. Changes in hemoglobin over past 4 weeks

- If haemoglobin decreases more than 1 g/dl over the past 4 weeks and current haemoglobin level is < 10.5 g/dl, the dosage may be raised by 25% of the last dose received by the subject (A).
- If haemoglobin decreases more than 1 g/dl over the past 4 weeks and current haemoglobin level is between 10.5 g/dl to 12.0 g/dl, the last dose received by the subject should be continued (B).
- If haemoglobin decreases more than 1 g/dl over the past 4 weeks but current haemoglobin is between 12.1 to 13.0 g/dl, the dose should be reduced by 25% of the last dose received by the subject (C).
- If haemoglobin decreases or an increase between 1.0 g/dl and current haemoglobin value is less than 10.5 g/dl, the dosage may be raised by 25% of the last dose received by the subject (D).
- If haemoglobin decreases or an increase between 1.0 g/dl and the current hemoglobin value is between 10.5 to 12.0 g/dl, the last dose received by the subject should be continued (E).
- If haemoglobin decreases or increase between 1.0 g/dl but the current haemoglobin is between 12.1 to 13.0 g/dl, the dose should be reduced by 25% of the last dose received by the subject (F).
- If haemoglobin increases more than 1 g/dl over the past 4 weeks and current haemoglobin is < 10.5 g/dl, the last dose received by the subject should be continued (G).
- If haemoglobin increases more than 1 g/dl over the past 4 weeks and haemoglobin level is between 10.5 to 12.0 g/dl, the last dose received by the subject should be continued (H).
- If haemoglobin increases more than 1 g/dl over the past 4 weeks but current haemoglobin is between 12.1 to 13.0 g/dl, the dose should be reduced by 25% of the last dose received by the subject (I).
- If current haemoglobin level is greater than 13.0 g/dl, not depending on the change of haemoglobin in the past 4 weeks, dose should be temporarily withheld until the haemoglobin begins to decrease between 10.5 and 12.0 g/dl, at which point therapy should be reinitiated at 25% reduced from the previous dose (J).

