9.6 Interim Analysis

An interim analysis will be conducted to evaluate the therapeutic equivalence of EPIAO with the standard treatment EPREX after a treatment period of 24 weeks. The analysis will be performed by an independent statistician, who is not involved in the trial conduct other than this interim analysis. The independent statistician will be unblinded and will conduct the analysis using actual treatment assignments. This interim analysis will be conducted after all the randomized patients complete the Visit 16 (Week 36/Day 252). The results of the interim analysis will be communicated to Independent sponsor representative. All other personnel involved in the study will remain blinded. The analysis will be performed in terms of efficacy, safety and immunogenicity between the treatment arms as per the final analysis stated in section 9.

The sponsor of the study wishes to use the data from the interim analysis to plan for registration of EPIAO in other countries where it is yet to be marketed. An interim report will be used to meet the requirement for local registration. A complete analysis will be conducted at the end of the treatment period.

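### The dose ANCOVA leaves out baseline weekly epoetin dose, the endpoint's own baseline, so a small gain in precision may be lost

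*Protocol*

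**What the plan says.** Protocol section 9.4.1 defines two co-primary endpoints, change in haemoglobin and change in weekly epoetin dose per kg, and gives both the same covariates. Its wording for the dose model is "weekly epoetin dosage per kg body weight baseline to 6-month treatment with EPIAO and EPREX with center, Hb level and weight as covariates". Identical covariates stand in the synopsis (Statistical Analyses): "baseline to 6 months treatment with EPIAO and EPREX with center, Hb level and weight as covariates". The resulting 95% CI is compared with ±45 IU/kg/week.

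Section 5.1.7 provides the missing covariate: "The stable dose of EPREX / EPIAO will be calculated as IU/kg/week before the start of the treatment period and captured in the eCRF". Section 9.8 names body weight and Hb level as stratification factors, with balance between the arms in Thailand and Russia. Baseline dose is not a stratification factor, and nothing else in the protocol adds it to the model.

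Section 9.6 has the unblinded 24-week analysis compare efficacy, safety and immunogenicity "between the treatment arms as per the final analysis stated in section 9", so the covariate list applies there too.

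**The concern.** The shared list suits the two endpoints unequally. For change in haemoglobin it contains Hb level, so that endpoint's own baseline is represented. For change in dose, nothing plays that part; weight and Hb level are not substitutes for baseline dose.

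A change score fixes the coefficient of the baseline at 1. ANCOVA with the baseline as covariate estimates it. When the true slope is below 1, the change score carries extra variance, and any chance difference in baseline dose between arms feeds into the treatment estimate.

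Balance is also less assured in the primary analysis set. Section 9.1 makes the per-protocol cohort primary, and sections 3.1.6 and 4.2.1 withdraw subjects who need more than 300 IU/kg/week, so membership of that cohort can itself depend on dose.

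What is at stake is the precision of one co-primary estimate. Section 9.6 says the interim results are meant for registration, so the estimate and its interval matter as well as the equivalence verdict.

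**Working it through.** **Inputs from the protocol.** 112 evaluable per group (section 9.8); margin ±45 IU/kg/week and a two-sided 95% CI (section 9.4.1). There is no SD, correlation or assumed true difference, so the figure of 112 cannot be reproduced. All variability inputs below are assumptions, shown as ranges.

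**1. General slope.** Write 6-month dose = a + b × baseline dose + error, with baseline SD s0 and between-arm baseline difference D.
- Variance of the change score without the baseline covariate: (1−b)² s0² + error variance.
- Variance with it: error variance.
- Variance saved: (1−b)² s0². Shift of the unadjusted estimate: −(1−b) × D. Both are zero at b = 1.

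**2. Closed form with equal SDs s at both times and correlation r (so b = r).** Change-score variance is 2(1−r)s²; adjusted variance is (1−r²)s²; their ratio is (1+r)/2; the CI is narrower by 1 − √ratio.

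| r | variance ratio | CI narrower by |
|---|---|---|
| 0.5 | 0.75 | 13.4% |
| 0.7 | 0.85 | 7.8% |
| 0.9 | 0.95 | 2.5% |

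**3. In IU/kg/week.** Half-width = 1.971 × SD × √(2/112), with √(2/112) = 0.1336 and baseline SD assumed 30–60.
- r = 0.5: SD of change 30–60 gives 7.9–15.8; adjusted 6.8–13.7.
- r = 0.9: SD of change 13.4–26.8 gives 3.5–7.1; adjusted 3.4–6.9.

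**4. Chance imbalance.** One standard error of the baseline difference is 30 to 60 × 0.1336 = 4.0–8.0. It shifts the unadjusted estimate by 2.0–4.0 at slope 0.5, 0.4–0.8 at slope 0.9 and 0 at slope 1. The largest of these is 4.0/45, about 9% of the margin.

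**5. With the planned covariates already in the model.** Simulation: 4000 trials, 112 per arm, 13 centres, 2 Hb bands, 3 weight bands, assumed weight–dose correlation −0.3. Variance ratios were 0.772, 0.878 and 0.969 at r = 0.5, 0.7 and 0.9, so the CI is 12.1%, 6.3% and 1.6% narrower. A repeat gave about 0.77, 0.87 and 0.94–0.97. At slope 1 the ratio was 1.008, which is no gain within simulation error.

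**6. Dose steps of the protocol's size.** Section 5.1.7 says that "an increase or decrease of 2000 IU per week is allowed for dose adjustment" and also describes changes of 25% of the last dose. A simulation of 300,000 subjects let dose move up or down at random, each with probability 0.1–0.3, at 2, 4 or 7 visits. Baseline mean/SD was 100/30, 100/50 or 120/60; mean weight was 65 kg (SD 13); dose was limited to 0–300, without rounding. The variance ratio was 0.985–1.000 for 2000 IU steps and 0.958–1.000 for 25% steps, so the CI is 0–2% narrower.

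**7. Effect on the verdict.** Power is the probability that the 95% CI lies within ±45, at 112 per arm. With SD of change 60 it is 99.97% at a true difference of 0, 99.5% at 8.5 and 97.1% at 13.917. The last two are the midpoint and upper limit of the interval cited in section 1.1.4 for another epoetin, a "95% CI for dosage of 3.086–13.917 IU/kg/week". With SD 30 it is about 100% at all three.

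**8. Scale check.** That cited interval has half-width (13.917 − 3.086)/2 = 5.4. For an assumed 50 to 250 subjects per arm this implies an SD of about 14–31, hence a half-width here of about 4–8.

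**The case against.** The strongest reply is that there is no error. The model is valid, it adjusts for the stratification factors and for centre, and the change score already subtracts baseline dose. Subjects enter on a stable EPREX dose, convert 1:1 and then move in limited steps, so the slope may well be near 1. The only calculation using those step sizes shows a gain of 0–2%, while the 13.4% and 7.8% figures rest on correlations the protocol does not give. A material power gain needs a much larger SD: 80% power at 112 per arm on dose alone implies an SD of change of 103.9, and adjustment would then raise power to 92.5%, 88.0% or 82.8% at r = 0.5, 0.7 or 0.9. But the 112 covers both co-primaries, and haemoglobin may be what drives it.

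Most of this stands, and it is why the point is minor. It does not remove the point. The slope is unknown: the 300 IU/kg/week limit, withholding above Hb 13.0 g/dl and investigator discretion could each pull it below 1. The step simulation is itself simplified, since its steps are random rather than driven by haemoglobin and it ignores rounding to 2000 IU multiples.

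The SAP was not available for this check and may already add the covariate. But the protocol prints a covariate list, and an SAP that follows it would omit baseline dose.

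**Conclusion.** The concern holds, as a minor one. The protocol fixes a dose model without the endpoint's own baseline, although that value is collected. The analysis remains valid.

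The likely loss lies between nothing (slope about 1, or 0–2% of CI width under steps of the protocol's size) and about 12–13% of CI width (correlation 0.5 with equal SDs). That range rests wholly on assumed SDs, correlations and step behaviour. No change in the conclusion against ±45 IU/kg/week is expected at SDs of change up to 60. Confidence in the size is medium because the slope is unknown.

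**What to change.** Add baseline weekly dose (IU/kg/week, the stable dose recorded before randomised treatment) as a continuous covariate in the dose ANCOVA, and keep centre, Hb level and weight.

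Record this before the unblinded 24-week analysis, so that the choice cannot appear to follow from the data. Section 1.5.3 allows changes to the planned analysis to be documented in an amendment, the SAP or both, so an SAP entry is enough. If section 9.4.1 and the synopsis are edited instead, section 10.8 requires the amendment to go to the ethics committee. The statistical cost is one degree of freedom, and no new data are needed.

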9.4.2 Secondary Efficacy Analyses

- Proportion of subject's hemoglobin values are within 10 - 12 g/dl for the last 4 weeks of the period for assessment of treatment efficacy and safety (Weeks 32-36)
- Proportion of subjects with any haemoglobin measurement outside the target range during the double-blind treatment period
- Mean hemoglobin and hematocrit levels every 4 weeks within treatment period (52 weeks)
- Mean doses of the study products (IU/kg/week) every 4 weeks throughout the study period (52 weeks)
- Incidence of blood transfusions

The appropriate descriptive statistics or frequency and percentages will be presented for the secondary end point. Other analysis will be carried out as deemed appropriate.

9.5 Safety Analyses

- Incidence and nature of adverse events
- Incidence of drug related adverse events
- Clinically significant changes in the vital signs, physical and laboratory examination
- Number of subjects who prematurely withdrew from the study due to AE and SAE
- Number of subjects with presence of anti-erythropoietin antibodies (anti-EPO Ab)

Safety will be assessed by physical examination, vital sign, laboratory test, immunogenicity and adverse event recording. Summary statistics will be provided for the laboratory, ECG, physical examination, immunogenicity and vital signs data. Frequency and percentage of the incidence of adverse event, nature of adverse event and incidence of drug related adverse event will be presented in the treatment group. Summary statistics will be presented for the occurrence of PRCA.

9.5.1 Adverse Event Analyses

All adverse events will be summarized in terms of severity, relation to study treatment, duration, action taken and subjects outcome. The number and the proportion of subjects who experienced AEs will be computed by treatment group, classified by Medical Dictionary for Regulatory Activities (MedDRA) Primary System Organ Class and Preferred Terms.

9.5.2 Clinical Laboratory Evaluation Analyses

Descriptive statistics, such as mean, standard deviation, median, minimum and maximum values will be provided for the continuous variables and the number of observations and percentage will be provided for the categorical variables.

9.5.3 Vital Sign Analyses

Descriptive statistics such as mean, standard deviation, median, minimum and maximum values will be presented.

9.5.4 Physical Finding Analyses

Descriptive statistics such as number of observation and percentage will be presented.

9.5.5 Concomitant Medications:

Proportion of subject who used concomitant medication during the study period will be computed by treatment group, classified by World Health Organization Drug Dictionary enhanced (WHO - DDE) Preferred Names. Concomitant medication will be coded using the WHO - DD enhanced version, classified by preferred names, and the categories tabulated and summarized.

